### 8.3 Waldenstrom's Macroglobulinemia Hematologic Response Criteria

CATEGORY	RESPONSE CRITERIA
Complete response (CR)	
 
Serum IgM values in normal range
 
Disappearance of monoclonal protein by immunofixation
 

Very good partial response (VGPR)	
 
Monoclonal IgM protein is detectable
 
At least 90% reduction of serum IgM from baseline or serum IgM values in normal range
 

Partial Response (PR)	
 
Monoclonal IgM protein is detectable
 
At least 50% but <90% reduction of serum IgM from baseline
 

Minor Response (MR)	
 
Monoclonal IgM protein is detectable
 
At least 25% but <50% reduction of serum IgM from baseline
 

Stable disease (SD)	
 
Monoclonal IgM protein is detectable
 
<25% reduction and <25% increase in serum IgM from baseline
 

Progressive disease (PD)	
 
≥25% increase in serum IgM with a total increase of at least 500 mg/dL from nadir 
 
Reconfirmation of initial IgM increase is required when IgM is sole criterion for PD confirmation.
 
 
 

1. Nadir is defined as the lowest serum IgM value obtained at any time from baseline onwards with the exception that serum IgM levels post-plasmapheresis will not be considered for up to 6 weeks.

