## OBJECTIVES

### 1.1.1 Title: Idelalisib for IgM-Associated AL Amyloidosis

### 1.1.2 Study Design:

This is a single arm, open label study designed to evaluate the safety and efficacy of idelalisib in patients with relapsed IgM-associated AL amyloidosis. Treatment will be comprised of idelalisib at 100mg orally twice daily, with permitted dose modifications for toxicity per manufacturer guidelines (Section 5). The medication will be continued until progression or significant toxicity.

After giving written informed consent, subjects will be evaluated for eligibility for enrollment in the study. Baseline evaluations will be performed as outlined in Section 7. Subjects who satisfy all inclusion and exclusion criteria will begin the study drug. Subjects will be monitored every cycle for safety and hematologic status. Organ function will also be measured during therapy.

Participants will be eligible to continue therapy as long as they do not demonstrate progressive disease or unacceptable toxicity. Standard response criteria for AL amyloidosis hematologic and organ response will be used (Gertz et al. 2010). Hematologic response will also be categorized and reported by Waldenstrom's macroglobulinemia hematologic response criteria. For the purposes of defining progressive disease, the amyloid response criteria will be used. Overall response rate will be measured and participants will be categorized into complete response, very good partial response, partial response and progressive disease. Progression free survival, organ response, safety and tolerability of idelalisib, and quality of life will be assessed.

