### 1.1.3 Patient population: (Specific inclusion and exclusion criteria are detailed in section 3)

### 1.1.4 Number of sites: 1, Boston Medical Center, [name]

### 1.1.5 Number of patients: 18 patients

### 1.1.6 Primary Objective:

- To determine the hematologic overall response rate (ORR) in IgM associated AL amyloidosis to a fixed dose of idelalisib. Response rates will categorized into complete response (CR), very good partial response (VGPR), partial response (PR) and progressive disease (PD) according to standard criteria (Gertz et al. 2010).

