#### 4.1.2 General Concomitant Medication and Supportive Care Guidelines

Participants will be required to take antibiotics for prevention of *Pneumocystis jiroveci* infection throughout the duration of the clinical trial. Participants will be instructed to take 1 tablet of Bactrim DS every Monday, Wednesday and Friday while taking idelalisib. If there is a concern for allergy or other adverse reaction to Bactrim DS in the opinion of the treating investigator, atovaquone 1500 mg daily may be prescribed instead.

Participants will be instructed not to take any additional medications (including over-the-counter products) during the course of the study without prior consultation with the investigator. At each visit, the investigator will ask the participant about any new medications he/she is or has taken after the start of the study drug.

Anti-emetics are permitted if clinically indicated. Standard supportive care medications are permitted. All concomitant medications/significant non-drug therapies taken  $\leq$  30 days prior to start and after start of study drug, including physical therapy and blood transfusions, should be recorded. The following restrictions apply during the entire duration of the study:

- No other investigational therapy should be given to participants.
- No anticancer agents other than the study medication should be given to participants. If such agents are required for a patient then the patient must first be withdrawn from the study.
- Growth factors (e.g. G-CSF, erythropoietin, platelet growth factors etc.) are not to be administered prophylactically but may be prescribed at the discretion of the treating physician for treatment related hematologic events in accordance with ASCO guidelines.
- Concurrent administration of idelalisib and strong CYP3A4/5 inhibitors (such as clarithromycin, ketoconazole, itraconazole, and ritonavir) and inducers (such as rifampin and rifabutin) should be avoided. Alternatives should be sought if possible. Provided there is no alternative treatment available, the Principal Investigator should be consulted, and treatment should be administered with caution; patients should be closely monitored for potential toxicities with temporary interruption of idelalisib. Examples are provided in Table 4-1.

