### 8.2 AL Amyloidosis Hematologic Response Criteria

CATEGORY	RESPONSE CRITERIA
Complete response (CR)	
 
Normal serum free light chain ratio
 
Negative serum and urine immunofixation electrophoresis
 

Very good partial response (VGPR)	
 
Difference in serum free light chains less than 40 mg/L
 

Partial Response (PR)	
 
>50% Reduction in the difference in serum free light chains
 

Stable Disease (SD)	
 
Meets neither criteria for CR, VGPR, PR or PD
 

Progressive Disease (PD)	
 
From CR, an increase in serum M-protein to > 0.5 g/dL, an increase in the urine M-protein to > 200 mg/day, or an increase in the serum monoclonal free light chain by > 10 mg/dL (100 mg/L). From VGPR, PR or SD, an increase in the serum M-protein from the lowest level by > 50%, as long as the absolute magnitude of this increase is > 0.5 g/dL; or an increase in the urine M-protein from the lowest level by 50%, as long as the absolute magnitude of this increase is > 200 mg/day; or an increase in the serum or urine monoclonal free light chain by > 50% from the lowest level, as long as the absolute magnitude is > 10 mg/dL (100 mg/L).
 

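### The plasmapheresis exclusion is tied to the Waldenstrom nadir and does not reach the amyloid rule that decides progression

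*Combined protocol and SAP*

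**What the plan says.** Section 8.3 defines Waldenstrom progression as a rise in serum IgM from nadir. Its footnote takes the nadir as the lowest value from baseline onwards, "with the exception that serum IgM levels post-plasmapheresis will not be considered for up to 6 weeks". This is the only mention of plasmapheresis in the protocol, and the word nadir appears only in the progression line of 8.3.

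Section 1.1.2 gives the Waldenstrom criteria a reporting role: "Hematologic response will also be categorized and reported by Waldenstrom's macroglobulinemia hematologic response criteria". It then states: "For the purposes of defining progressive disease, the amyloid response criteria will be used".

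The progression line of 8.2, for a patient in VGPR, PR or SD, includes "an increase in the serum M-protein from the lowest level by" more than 50%, provided the absolute increase exceeds 0.5 g/dL. A parallel route uses serum or urine free light chain, with a 50% rise and a 100 mg/L threshold. Neither route excludes post-exchange values.

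Under 8.5, objective progression is a PFS event. Section 4 neither names nor prohibits plasmapheresis. Section 4.1.2 asks for significant non-drug therapies to be recorded.

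**The concern.** The footnote shows that the authors regarded an IgM value drawn soon after an exchange as an unreliable reference for progression. They attached that judgement to a progression rule that does not decide progression in this trial. The rule that does decide it takes the lowest observed value as its reference, whatever produced it.

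At stake is a false PFS event in a patient whose disease has not changed, in a study of at most 18 patients. The response lines of 8.3 are also unprotected, because the footnote qualifies only the nadir. A trough can therefore be reported as a Waldenstrom response.

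**Working it through.** The plan gives no figure on this point, so there is none to reproduce. The check applies its own thresholds.

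**Inputs.** From 8.2: PD needs a rise above 50% from the lowest level and an absolute rise above 0.5 g/dL. From 8.3: PD needs a rise of at least 25% and at least 500 mg/dL from nadir; PR is a fall of at least 50% but under 90% from baseline. Assumed for illustration: baseline M-protein B, a fraction f missing when the trough is sampled, and a return to B with no change in disease.

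**When 8.2 calls this progression.** The trough is B(1 − f) and the rebound is fB.

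- Relative condition: f/(1 − f) > 0.5, so f > 1/3.
- Absolute condition: fB > 0.5 g/dL, so B > 0.5/f.

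| f | Rise from trough | B needed (g/dL) | PD under 8.2 possible? |
|---|---|---|---|
| 0.30 | 43% | – | no |
| 0.34 | 52% | > 1.47 | yes |
| 0.40 | 67% | > 1.25 | yes |
| 0.50 | 100% | > 1.00 | yes |
| 0.70 | 233% | > 0.71 | yes |

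Because f cannot exceed 1, the absolute condition always fails when B is 0.5 g/dL or less. Section 3.1.5 admits patients with IgM paraprotein above 0.5 g/L, which is 0.05 g/dL, or on free light chains alone. Some enrolled patients are therefore out of reach of this route.

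**One case under both sets of criteria.** Take M-protein of 1.5, then 0.7 after an exchange, then 1.5 g/dL. For simplicity, treat it as equal to serum IgM (1,500, 700, 1,500 mg/dL).

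- Fall: (1.5 − 0.7)/1.5 = 53%. Rebound: (1.5 − 0.7)/0.7 = 114%, or 0.8 g/dL.
- Under 8.3 with its footnote, the trough is set aside, the nadir stays at 1,500 mg/dL, the rise is zero and there is no PD.
- Under 8.2, 114% exceeds 50% and 0.8 exceeds 0.5 g/dL, so a patient in SD has PD and a PFS event.
- Under the response lines of 8.3, the 53% fall is a Waldenstrom PR.

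Section 8.3 also requires reconfirmation when IgM is the only criterion, and 8.2 does not. Reconfirmation would not repair this case: the rebound value is genuine and would repeat. The fault lies in the reference value.

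**Free light chain route.** If the 100 mg/L threshold is read as the size of the increase, the same algebra gives f > 1/3 and f × (baseline light chain) > 100 mg/L; at f = 0.5, a baseline above 200 mg/L. The documents do not say how far an exchange lowers light chains, so this route is open in the text but cannot be illustrated from it.

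**Primary response.** The objective is "To determine the hematologic overall response rate (ORR) in IgM associated AL amyloidosis to a fixed dose of idelalisib", classified by the amyloid categories. Amyloid PR is a more than 50% "Reduction in the difference in serum free light chains"; VGPR is "Difference in serum free light chains less than 40 mg/L"; CR needs a normal light chain ratio and negative immunofixation. The worked case changes M-protein only, so it adds no primary responder.

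**The case against.** The strongest reply is that the reach is small and the consequence softened. Exchange is not planned anywhere in sections 3, 4 or 7. A patient must have one, enough M-protein must be missing at a sampled visit (months 1 and 2, then every three months in the study calendar), and baseline must be high enough. Sections 4.1.3 and 5.1.1 let a participant who meets progression criteria stay on drug at the Principal Investigator's discretion if judged to benefit. All of this stands and sets the severity. It does not remove the defect, because staying on drug does not undo the PFS event.

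Three stronger readings are tempting and are not supported.

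- *That the protocol expects or permits plasmapheresis.* One footnote in a criteria table contemplates it. The line "Standard supportive care medications are permitted" concerns medications, not procedures. The accurate statement is that exchange is neither named nor prohibited.
- *That an exchange endangers the primary test.* A reader might feed a false responder into the two-stage rule of 12.2, where one response in 9 and three in 18 are decisive. That presumes the light chain difference falls by more than 50%, or below 40 mg/L, at a sampled visit. The documents give no figure for that or for how often exchange occurs, so any resulting error rate would rest on the presumption.
- *That false progression necessarily stops treatment.* The discretion just described means that it need not.

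**Conclusion.** The gap is real and minor. Followed exactly, 8.2 turns a post-exchange rebound to an unchanged baseline into progression and a PFS event, whereas the footnote in 8.3 would set the same trough aside. The M-protein route needs a fall above one third and a rebound above 0.5 g/dL, and so a baseline above 0.5 g/dL. A post-exchange trough can also be reported as a Waldenstrom response, which is a descriptive output here.

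The conclusion rests on an exchange taking place and its trough being sampled. The values in the example are illustrative. The expected number of affected patients cannot be derived from the documents and is likely to be small. No effect on the primary response rate is shown.

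**What to change.** Add one rule to 8.1 that governs both 8.2 and 8.3: *serum M-protein, IgM and free light chain values drawn within 6 weeks after plasmapheresis are not used as the lowest level, including a baseline value that would serve as the lowest level, or to establish response; they may establish progression if they meet the criteria against a valid earlier low.* The 6 weeks is the protocol's own window. Copying the IgM-only footnote into 8.2 would leave free light chains uncovered.

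The rule should not bar these values from establishing progression. A post-exchange value is biased downward, so one that still meets PD is credible; discarding it would delay true progression and lengthen PFS.

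Take exchange dates from the non-drug therapy record in 4.1.2. That record looks back 30 days before the start of study drug, short of 6 weeks (42 days), so exchanges before baseline need a specific question.

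The cost is one sentence of amendment. An exchanged patient's response may go unclassified until the next scheduled value outside the window, which can be three months away, or longer with repeated exchanges. No treatment or visit changes.

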#### 8.4 Organ Response Criteria

A subject will be said to have had an organ response in an involved organ if any of the following criteria are met.

- Kidney: 50% reduction in 24-hour urine protein excretion in the absence of progressive renal insufficiency (defined as a 25% increase in serum creatinine, as long as that is  $>$  to an absolute increase of 0.5 mg/dL). In the case of nephrotic syndrome: a decrease in proteinuria to  $<$  1g/24h and an improvement in one of 2 extrarenal features – normalization of serum albumin or resolution of edema and/or discontinuation of diuretics in response to improvement in edema.
- Heart:  $\geq$  2 mm reduction in the interventricular septal (IVS) thickness by echocardiogram, improvement of ejection fraction by  $\geq$  20% (echocardiogram must be performed at the same institution), or decrease in 2 NYHA classes without increase in diuretic need.
- Liver:  $\geq$  50% decrease in normalization of an initially elevated alkaline phosphatase level or reduction in the size of the liver by at least 3 cm if assessed by imaging.
- Neuropathy: While neurotoxicity is acceptable for determining organ involvement, it will not be adequate for assessing organ response; organ response will be indeterminable for subjects in which neurotoxicity is the only site of organ involvement.
- Gastrointestinal Tract: While GI involvement is acceptable for determining organ involvement, it will not be adequate for assessing organ response: organ response will be indeterminable for subjects in which GI is the only site of organ involvement.

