### 1.1.7 Secondary Objectives:

- To assess progression free survival (defined as the interval from the first documentation of CR, VGPR or PR to the earlier of the first documentation of disease progression)
- To determine organ response (defined as improvement of involved organ function i.e. eGFR for kidneys, EF for heart etc.)
- To assess the safety and tolerability of idelalisib
- To measure impact on QOL of life using SF-36 assessment tool.

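### The nephrotic-syndrome kidney response rule in section 8.4 has no creatinine condition, so on two of its three readings a patient with worsening kidney function counts as a responder

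*Combined protocol and SAP*

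**What the plan says.** Section 8.4 opens with a general rule: "A subject will be said to have had an organ response in an involved organ if any of the following criteria are met". A list by organ follows, and the kidney bullet holds two sentences.

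- **First sentence.** It asks for a "50% reduction in 24-hour urine protein excretion in the absence of progressive renal insufficiency". That exclusion is defined as a 25% rise in serum creatinine that is also more than "to an absolute increase of 0.5 mg/dL".
- **Second sentence.** It starts "In the case of nephrotic syndrome: a decrease in proteinuria to" below 1 g/24h and also requires "an improvement in one of 2 extrarenal features": albumin back to normal, or edema resolved and/or diuretics stopped because edema improved. It mentions neither creatinine nor eGFR and does not refer back to the exclusion.

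Section 1.1.7 states the objective in other terms: "To determine organ response (defined as improvement of involved organ function i.e. eGFR for kidneys, EF for heart etc". Section 12.1 lists organ response as a secondary endpoint. Section 12 attaches no test, alpha or threshold to it and gives no further scoring rule. The progression criteria in section 8.2 are hematologic only, so nothing there restores a renal-function condition.

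**The concern.** Urine protein can fall because filtration falls, and the creatinine condition in the first sentence keeps such patients from being counted as improved. If the condition does not reach the nephrotic sentence, part of the kidney response rate could be loss of kidney function reported as benefit. The study is single-arm, so no control group would show the same error.

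Rising creatinine is foreseeable in this trial. Section 3.2.2 excludes only GFR below 15 ml/min, section 2.1.6 lists acute renal failure among the most frequent serious events in the dose-escalation and extension studies, and section 6.2.3 lists creatinine elevation as a toxicity of the default prophylactic antibiotic. None of this shows how often creatinine would rise in a patient whose proteinuria also falls below 1 g/24h.

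**Working it through.** The plan gives no figure to reproduce here, so the check applies the two sentences to hypothetical patients.

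**Rules**
- Renal insufficiency (RI): creatinine rise of at least 25% and more than 0.5 mg/dL.
- Sentence 1 (S1): urine protein down by at least 50%, and not RI.
- Sentence 2 (S2): urine protein below 1 g/24h, and one extrarenal feature.

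**Patients (both nephrotic, both invented)**
- A: protein 6 to 0.8 g/24h, edema resolved, creatinine 1.5 to 3.5 mg/dL. Protein fall = (6 − 0.8)/6 = 87%. Creatinine rise = 2.0 mg/dL, and 2.0/1.5 = 133%, so RI is met. S1 fails and S2 is met.
- B: protein 8 to 4 g/24h, creatinine stable. Protein fall = (8 − 4)/8 = 50%, no RI. S1 is met and S2 fails.

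| How S2 relates to S1 | A | B |
|---|---|---|
| Alternative (S1 or S2) | responder | responder |
| Replacement (S2 only) | responder | non-responder |
| Added requirement (S1 and S2) | non-responder | non-responder |

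The three readings give three different results, and A is a responder on two of them.

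**Where the split begins.** From a baseline creatinine of 1.5 mg/dL, a rise to 1.9 is +0.4 (0.4/1.5 = 27%). The absolute limit is not passed, so a patient with proteinuria 6 to 0.9 g/24h and normalized albumin meets both sentences. A rise to 2.1 is +0.6 (0.6/1.5 = 40%). RI is met, S1 fails, and S2 still scores a response.

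**Whom S2 adds under the alternative reading.** Assume nephrotic baseline proteinuria is at least 2 g/24h; the protocol gives no threshold. A value below 1 g/24h is then less than 1/2 of baseline, so the fall always exceeds 50%. A patient who meets S2 can therefore fail S1 only through RI, and every responder that S2 adds has RI. With a baseline under 2 g/24h this step no longer holds.

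**Effect per patient.** Section 1.1.5 plans 18 patients. One reclassified patient moves the rate by 1/18 = 5.6 points over all of them. The number with renal involvement is not given. If it is 10, the shift is 1/10 = 10 points; if 6, it is 1/6 = 17 points.

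**Section 8.4 against section 1.1.7.** Patient A's creatinine more than doubled, so eGFR fell and the objective's wording would not call A improved. Patient B's creatinine did not change, so the same wording would not call B improved either, although S1 does. The two sections measure different things.

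**The case against.** The strongest reply is that the text is silent rather than wrong. The nephrotic sentence follows the creatinine condition inside the same bullet and can be read as a further demand on nephrotic patients. The condition then still applies and patient A is not a responder. The general rule at the top of section 8.4 introduces a list by organ, so it does not clearly split two sentences within one bullet. An alternative that admits only patients whom the previous sentence has just rejected is also an unlikely intention. This stands in part. A reader might infer that A is a responder however the bullet is read, or that section 8.4 plainly contradicts itself; the documents do not support either. Replacement, however, remains a natural reading of a sentence introduced for the nephrotic case, and it also scores A as a responder.

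Section 1.1.2 says standard published criteria will be used for organ response. Those criteria are not reproduced beyond section 8.4, so they cannot be used here to decide the question, and it cannot be claimed that section 8.4 departs from them.

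It is also fair to say that few patients will meet every condition at once: protein below 1 g/24h, an extrarenal feature, and a creatinine rise past both limits. The entry limit on GFR describes baseline function and says nothing about decline on study. Creatinine is collected repeatedly, so kidney responders could in any case be reported alongside their creatinine change. These points limit the weight of the concern but do not settle how a given patient is to be scored.

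**Conclusion.** The concern holds as an unresolved scoring rule. Section 8.4 ties its renal-insufficiency condition to one of two kidney sentences and does not say how the two combine. On two of three readings, a nephrotic patient with progressive renal insufficiency by the protocol's own definition is a kidney responder.

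The per-patient shifts rest on one misclassified patient; the larger ones also rest on an assumed 6 to 10 patients with renal involvement. The statement that the nephrotic sentence adds only patients with renal insufficiency rests on the alternative reading and on the assumed 2 g/24h baseline. A reader might go further and infer that the reported kidney response rate will be materially inflated. The documents do not support that, because they give no frequency for such patients.

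Nor is the trial's main conclusion at risk: the success rule in section 12.2 concerns the primary hematologic response. Severity: minor.

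**What to change.** 1. In section 8.4, state that the existing creatinine condition (25% increase, with an absolute increase above 0.5 mg/dL) applies to both kidney sentences. Patient A is then a non-responder on every reading.
2. Before analysis, have the sponsor state how the two sentences combine for nephrotic patients. The first change does not settle patient B. With the condition on both sentences and a baseline of at least 2 g/24h (assumed), replacement and added requirement give the same answer, while under the alternative reading the nephrotic sentence adds nobody. The remaining question is whether a 50% fall is enough for a nephrotic patient or the 1 g/24h limit plus an extrarenal feature is needed. The documents do not decide this, and the choice belongs to the sponsor.
3. Reconcile the eGFR wording in section 1.1.7 with the proteinuria criteria in section 8.4.

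The cost is a few sentences. Creatinine, albumin and 24-hour urine protein are already in the section 7 calendar, and no visit or sample-size figure changes. The kidney response rate may be slightly lower.
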